### 8.5.3 Exploratory Analyses (or Analyses of Exploratory Endpoints)

- To characterize antibody responses to a broad panel of antigens, sera will be collected at baseline, prior to RP, and 9 weeks following RP, and profiled using spotted antigen array (50). After standard preprocess of the protein array data, Cluster and Tree view software will be used for unsupervised clustering of the data with Pearson correlation and complete linkage. For each array, an antigen is identified as being detected if its value is above the median. To determine the number of up- and down-modulated antibodies, the difference in log2 intensity values of pretreatment and post-treatment samples will be taken for each patient to identify antigens that are detected differentially due to treatment.
- Assessment of change from baseline in antigen-specific T-cell immunity in the blood will be performed using repeated measure analysis of variance (ANOVA) methods with a mixed model approach to allow for a varying number of follow-up measurements. To study the change from baseline (screening visit) to post-baseline visits (up to 9 weeks post-RP), the mixed model will include four visits (up to 9 weeks post-RP) and subject as a random effect. Using polynomial contrast statements, the overall pattern T-cell immunity in the blood (e.g. linear) will be investigated. The specific comparison of change in immunity between baseline and any specific post-baseline time point will be tested also using linear contrast statements. The above analysis will be done for each arm separately as well as aggregate.
- Development of and changes in humoral immune responses in the periphery following treatment. This will be evaluated by testing serum with methods such as:
  - Measurement of antibodies to PSA, TAA and the viral vector may be performed using peptide/protein arrays, standard ELISA assays or flow cytometry to determine neutralizing antibody titers. After standard pre-process of the protein array data, Cluster and Tree view software will be used for unsupervised clustering of the data with Pearson correlation and complete linkage. For each array, an antigen is identified as being detected if its value is above the median. To determine the number of up- and down-modulated antibodies, the difference in log2 intensity values of pre-treatment and post-treatment samples will be taken for each patient to identify antigens that are detected differentially due to treatment.

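### The array detection rule in section 8.5.3 marks about half of all antigens as detected in every serum, so the number detected cannot show new antibody responses

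*Combined protocol and SAP*

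**What the plan says.** Section 8.5.3 describes the array analysis twice in nearly the same words, once for a broad antigen panel and once for antibodies to PSA, tumor-associated antigens and the viral vector. For the broad panel, "sera will be collected at baseline, prior to RP, and 9 weeks following RP, and profiled using spotted antigen array".

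Both paragraphs then have these steps:

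- Preprocessing: "After standard preprocess of the protein array data", with no description of the normalisation.
- Detection, array by array: "an antigen is identified as being detected if its value is above the median". No blank, negative-control spot, reference serum or pre-treatment threshold is named.
- Change: "To determine the number of up- and down-modulated antibodies", the plan says that "the difference in log2 intensity values of pretreatment and post-treatment samples will be taken for each patient to identify antigens". The stated purpose is to "identify antigens that are detected differentially due to treatment". No size of difference, test or error rate is given.

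The second paragraph also allows "standard ELISA assays or flow cytometry to determine neutralizing antibody titers", as an option. Section 2.4.3 lists both the development of humoral responses and changes in them as an exploratory endpoint.

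**The concern.** A detection rule should separate signal from background. A threshold set at the middle of the same array cannot do so, because it moves with the data it is meant to judge. The number detected is fixed before any serum is tested.

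This matters most for the PSA, tumor-antigen and vector arrays. There, a rise across many spots is what vaccination might produce; section 1.2.2 reports that anti-vaccinia titers increased after PROSTVAC. Yet the rule would call half of the spots detected at baseline, and also in Arm B, which receives no vaccine (section 3.1). Whether a response has developed is a question of absent before and present after, and this is the only such call that the plan defines for the arrays.

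The second step attributes differences to treatment without saying how large a difference must be or how chance findings among many antigens are limited. A count of modulated antibodies reported on that basis would be hard to interpret.

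**Working it through.** The plan gives no sample size, power or error rate for this analysis, so there is no figure of its own to reproduce.

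**1. Share detected (algebra).** For m distinct values on one array, exactly floor(m/2) lie strictly above their own median. With m = 1000 that is 500, or 50.0%. With m = 8001 it is 4000, or 49.99%. Also, median(x + c) = median(x) + c, so a rise of c log2 units in every antigen leaves the detected set unchanged. Because the count is the same before and after, every newly detected antigen is matched by one newly lost.

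**2. Simulation of one patient's pre and post arrays.** The documents give no array size, intensity distribution or noise level. Assumed inputs: 1000 antigens; log2 intensity with mean 8 and SD 1.5; noise SD 0.3 added to the post value; and, because the plan has no cut-off, 1 log2 unit to count an antigen as raised.

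| True change (log2 units) | Detected, pre and post | Newly detected / newly lost | Mean difference, not centred | At least 1, not centred | Mean difference, centred | At least 1, centred |
|---|---|---|---|---|---|---|
| None | 50.0%, 50.0% | 32 / 32 | -0.01 | 0.1% | -0.02 | 0.0% |
| +1 in all | 50.0%, 50.0% | 29 / 29 | 1.01 | 51.4% | 0.04 | 0.1% |
| +2 in all | 50.0%, 50.0% | 29 / 29 | 1.98 | 99.6% | -0.01 | 0.2% |
| +1 in 60% | 50.0%, 50.0% | 70 / 70 | 0.60 | 30.2% | -0.02 | 1.2% |
| +2 in 10% | 50.0%, 50.0% | 47 / 47 | 0.19 | 10.0% | 0.06 | 10.0% |

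Centred means that each array's own median is subtracted first. Runs with 100 and 8001 antigens gave the same pattern.

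- The detected share is the same in every row.
- Without centring, the log2 difference shows a general rise clearly.
- With centring, a general rise disappears. In the 60% row, centring also puts 4.5% of antigens at -1 or lower although none truly fell.
- A rise confined to 10% of antigens is found either way.

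**3. Changes of status from noise alone.** For two bivariate-normal measurements with test-retest correlation rho and no treatment effect, the chance of falling on opposite sides of the two medians is arccos(rho)/pi:

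- rho = 0.80: 20.5%
- rho = 0.90: 14.4%
- rho = 0.95: 10.1%

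The simulation's inputs imply rho = 1.5/sqrt(1.5² + 0.3²) = 0.98. That gives arctan(0.3/1.5)/pi = 6.3%, in line with the (32 + 32)/1000 = 6.4% in the first row. All of these correlations are assumptions.

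**4. The log2 step without a cut-off.** If the sign of the difference alone decided the label, then with no effect and symmetric noise about half of the antigens would be labelled up and half down. The plan does not say that sign alone decides; it gives no rule.

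**The case against.** The strongest reply is that the detection call is not the plan's measure of treatment effect. The next sentence takes a continuous paired log2 difference, which does show a general rise if arrays are not centred on their own medians, and nothing in the documents says that they will be. ELISA or flow cytometry may also be used, and neither depends on an array median. Even under the median rule, a single antigen that rises selectively can cross the median and become newly detected. The array method is cited to a publication that may define the steps more fully. The analysis is exploratory, with no stated hypothesis test.

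Much of this stands, and it rules out two stronger readings:

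- A reader might infer that no general treatment-induced rise can show anywhere in the humoral analysis, or that the endpoint cannot be measured at all. The documents do not support that. The limit applies to the detection call and, only if preprocessing centres each array, to the log2 difference as well.
- A reader might take the 20.5%, 14.4% and 10.1% rates as the share of antigens that the plan will falsely attribute to treatment. The plan does not clearly say that it will count changes of detected status, and the rates rest on assumed correlations.

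The reply does not rescue the detection rule. Selective crossings leave the total unchanged, since each gain displaces another antigen. The other assays are optional. The log2 step still lacks a threshold, a test and error control, and whether it can show a general rise depends on a normalisation that the plan leaves open.

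**Conclusion.** The detection rule, as stated in both array paragraphs, cannot do its job. On the natural reading it fixes the detected share at about 50% per array whatever treatment does, so the number detected cannot rise or document new antibody responses. This follows by algebra and needs no assumption about noise. It would fail only if the median meant something else, such as that of negative-control spots, and the text names no such reference.

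The paired log2 difference remains usable, subject to the normalisation, but as written it does not support attributing changes to treatment. The simulated sizes and the rates of status change are illustrations under assumed inputs.

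The point is worth correcting because a stated rule is unfit and the repair is cheap. It does not touch the primary endpoint, the sample size or the safety analyses.

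**What to change.** In both array paragraphs of section 8.5.3:

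- Define detection by one fixed cut-off applied to both pre and post samples, preferably from the array's negative-control signal. A percentile of screening sera is a weaker alternative: a 95th percentile sets baseline positivity near 5% per antigen by construction and, with 42 patients, rests on about two sera (0.05 × 42 = 2.1).
- State the normalisation, and choose one that does not centre each array on its own median.
- Call an antibody modulated only at a pre-set fold change, for example an absolute log2 difference of at least 1, with a paired test across patients and false-discovery-rate control. State which of the two later sera is the post-treatment sample.

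The cost is plan wording and re-coding of the call. No new samples are needed, because the sera are already to be collected and profiled. The downside is that fewer antigens will be called detected or modulated.

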## Abstract

[figure not shown]
Title	An open-label, randomized phase II trial of PROSTVAC and ipilimumab (as monotherapy and in combination) as neoadjuvant treatment for men with localized prostate cancer (PC) undergoing radical prostatectomy (RP).
Patient population	Prostate cancer patients undergoing RP
Rationale for Study	
30-40% of patients who undergo RP with curative intent for their localized PC experience relapse of their disease. Therefore, improved therapeutic approaches are needed in this patient population. Enhancing the immune system's response to the tumor may improve long-term outcomes following RP.
 
PROSTVAC is a vaccine therapy consisting of two recombinant viral vectors that may generate systemic immune responses to PSA, and has been shown to improve overall survival in a randomized, placebo-controlled and blinded phase II trial. PROSTVAC is well tolerated, with most adverse events (AEs) related to mild injection site reactions and only a subset of patients showing other mild systemic AEs such as fatigue.
 
CTLA-4 is negative regulatory molecule that is upregulated when the antigen-specific T-cell is activated, which may blunt the immune system's response to malignancy. ipilimumab is a human anti-CTLA-4 monoclonal antibody designed to stimulate immune responses. It has obtained regulatory approval for the treatment of metastatic melanoma, and demonstrated clinical activity in prostate cancer.
 
We hypothesize that PROSTVAC and ipilimumab can each induce specific immune response in the primary tumor as well as in peripheral blood, and that in combination, IPILIMUMAB may augment the T cell-mediated immune response generated by PROSTVAC by blocking the inhibitory signal of the CTLA-4 checkpoint.

Primary Objective	
 
To assess the immunologic impact induced within the prostate by neoadjuvant administration of PROSTVAC OR ipilimumab OR the combination in men with localized PC undergoing RP, as measured by CD3+ T cell tumor infiltration.
 

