### **3.6 Randomization Procedures**

Once patients have signed the informed consent, patients will be randomized 1:1:1 by stat computing software R, package blockrank, to receive PROSTVAC alone, Ipilimumab alone, or the combination. The randomization is done within blocks to ensure that the balance between treatments stays close to equal throughout the trial. Randomization must be completed within 28 days of day 1 of study.

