### 8.5.2 Secondary Analyses (or Analyses of Secondary Endpoints)

- T cell tumor infiltration (of selected T cell subsets) will be scored by IHC assessment, and scored by the number of T cells/ $\mu\text{m}^2$ . Therefore, the number of T cells will be normalized per unit area. The change in T cell infiltration following neoadjuvant therapy will be determined as described above for the primary endpoint. Similar analyses may be performed for other immune cells, such as CD4+, CD8+, CD56+, FOXP3, etc. Results will be reported as described for the primary endpoint, and T cell infiltration will be reported separately for areas of tumor interface, tumor center and benign tissue.
- Flow cytometry will be performed in both pre- and post-treatment peripheral blood mononuclear cells (PBMC) to determine the change in T cell activation (both  $\text{T}^{\text{reg}}$  and  $\text{T}^{\text{effector}}$  cells) after neoadjuvant therapy. Descriptive statistics for continuous measurements will be used to summarize the changes.
- Treatment-related toxicities will be assessed according to NCI CTCAE v4.03, for all patients who receive at least a single dose of investigational therapy. The distribution for the

maximum observed grade for each adverse event will be tabulated and reported with 95% confidence interval.

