  - Measurement of cytokines, chemokines or cancer biomarkers by Luminex multiplex analysis will be summarized by descriptive statistics for continuous variables at each timepoint for each arm. Furthermore, repeated measure ANOVA methods with a mixed model approach to allow for a varying number of follow-up measurements will be applied. The specific comparison of change between baseline and any specific post-baseline time point will be tested also using linear contrast statements.
  - PD-L1 expression, by IHC assessment, will be scored on a 0-3 scale (0=0-5% staining, 1=6-33% staining, 2=34-66% staining, 3=67-100% staining). For each subject, the change in PD-L1 expression score following neoadjuvant therapy will be calculated for exploratory characterization of the impact on PD-L1 in localized prostate cancer. Descriptive statistics for categorical measurements will be used to summary the PD-L1 expression change for each location. Furthermore, univariate analysis (proportion test) will be applied to explore the PD-L1 expression score change between locations.
- In order to assess the clinical impact of neoadjuvant treatment with PROSTVAC, ipilimumab, or the combination or PROSTVAC and ipilimumab:

- The proportion of patients who achieve a  $\geq 30\%$  decline in PSA at the time of RP will be reported with 95% confidence intervals.
- The proportion of patients with pathologic complete response (pT0) at the time of RP will be reported with 95% confidence intervals.
- T-cell receptor (TCR) repertoire sequencing following re-stimulation on T cells in vitro with prostate specific, tumor associated antigens and vector specific antigens to evaluate clonality of T-cell responses in the periphery. The responses in the tumor may also be evaluated in prostate biopsy samples to allow correlation with responses in the periphery. For each individual treatment, the change in tumor-infiltrating TCR between pre-treatment and post-prostatectomy after treatment will be assessed by calculating the number of unique clonotypes comprising the top 25th percentile of cumulative reads after sorting by clone abundance. Repertoire change between sequencing experiments will be measured using Morisita's distance.

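### No between-arm comparison is specified for the blood immune endpoints, so the randomised combination-versus-PROSTVAC contrast is not planned in blood

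*Combined protocol and SAP*

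**What the plan says.** Section 3.6 states that "patients will be randomized 1:1:1" to PROSTVAC (Arm A), ipilimumab (Arm B) or both (Arm C). The Abstract gives a two-part hypothesis. The first part is "We hypothesize that PROSTVAC and ipilimumab can each induce specific immune response in the primary tumor as well as in peripheral blood". The second is that "in combination, IPILIMUMAB may augment the T cell-mediated immune response generated by PROSTVAC".

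The three blood endpoints are handled as follows.

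- **Antigen-specific T cells (8.5.3, exploratory).** A repeated-measures mixed model with four visits and a random subject effect. The named contrasts are polynomial trends over visits and baseline against later visits. The paragraph closes: "The above analysis will be done for each arm separately as well as aggregate".
- **Luminex cytokines, chemokines and biomarkers (8.5.3, exploratory).** Descriptive summaries by time point and arm, then a mixed model: "The specific comparison of change between baseline and any specific post-baseline time point will be tested also using linear contrast statements". How arm enters that model is not stated.
- **Flow cytometry of T cells (8.5.2, secondary).** "Descriptive statistics for continuous measurements will be used to summarize the changes". No split by arm is stated.

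For tissue CD3+ response, Section 8.5.1 also announces an analysis by arm and in aggregate. It then adds a test of the combination against the pooled monotherapies and pairwise tests among the three arms. Section 8.5.2 carries that reporting over to the tissue subsets.

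**The concern.** Whether ipilimumab changes the response to PROSTVAC is a between-arm question, and Arm A is the randomised control for it. Arm B gets no vaccine, so it is the concurrent control for PSA- and vector-specific responses. Fits run arm by arm with baseline contrasts use neither control.

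Two things are at stake. First, the planned tests invite a statement about the combination based on which arms reached significance, and that is not a test of a difference. Second, a change over time that is not due to drug (assay drift, visit conditions) enters a within-arm or aggregate contrast as if it were treatment effect, whereas it cancels between arms sampled on the same schedule. The 12-patient reference cohort in Section 8.6 cannot fill this gap: it is chosen on consent to use prostatectomy specimens, and no blood sampling is described for it.

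**Working it through.** **Inputs.** 13 evaluable patients per arm and a significance level of 0.10, sidedness not stated (Section 8.2). Sampling at screening, before RP and 9 weeks after RP (Section 7.1.2.2). RP on Day 57 in Arms A and C and Day 43 in Arm B (Section 6.1.4). No SD, effect size or power is given for any blood endpoint, so effects below are in SDs of the change from baseline, assumed normal, and a range is shown.

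**The plan's own figures.** These concern tissue only. Power for 66% against 20% with 13 per group at two-sided 0.10 comes to 79.3%, against the stated 80%. Total size is 39 / (1 − 0.07) = 41.9, rounded up to 42. Both reproduce.

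**Step 1: 8.5.1 against 8.5.3.** Both sections announce an analysis by arm and in aggregate. 8.5.1 goes on to name between-arm tests; 8.5.3 names none for blood.

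**Step 2: within-arm significance as a stand-in.** Let two arms have the same true change of d SD. Each one-sample t-test with n = 13 has power p from the noncentral t distribution (12 df, noncentrality d√13). The chance that exactly one arm is significant is 2p(1 − p).

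| True change d | p at 0.05 | Exactly one arm, 0.05 | p at 0.10 | Exactly one arm, 0.10 |
|---|---|---|---|---|
| 0.3 SD | 0.169 | 28% | 0.270 | 39% |
| 0.5 SD | 0.382 | 47% | 0.522 | 50% |
| 0.8 SD | 0.754 | 37% | 0.858 | 24% |

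For example, at d = 0.5 and level 0.05: 2 × 0.382 × 0.618 = 0.472. A direct C − A test would be wrong in 5% (or 10%) of such trials.

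**Step 3: the aggregate fit.** If a vaccine-specific response changes by δ in A and C and by nothing in B, the aggregate mean change is (13δ + 13δ + 0) / 39 = 0.67δ, which describes no arm. If instead all arms share a non-drug change of 0.3, 0.5 or 0.8 SD, the aggregate test (n = 39, two-sided 0.05) rejects in 45%, 86% or more than 99% of trials.

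**Step 4: what a direct contrast can deliver.** For C − A with 13 against 13, power at two-sided 0.05 is 23% at 0.5 SD, 50% at 0.8 SD, 69% at 1.0 SD and 80% at 1.15 SD. At two-sided 0.10, 80% power needs about 1.0 SD. The 95% CI half-width is about 2.064 × √(2/13) = 0.81 SD.

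**The case against.** The strongest points on the other side are these.

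- **The quoted sentence covers one endpoint.** This stands. It governs the antigen-specific T-cell model only. The Luminex model does not mention arm, and flow cytometry states no split.
- **A reader might infer that the arms are never compared in blood, or that comparison is excluded.** The documents do not support that. 8.5.1 uses similar wording and still adds comparisons; 8.5.3 lists terms the model will include without saying that these are all; Luminex summaries by arm can be set side by side. Section 8.5 also mentions two-sample tests in general terms, but in the paragraph on baseline summaries and with no endpoint or grouping named. The supportable claim is that no comparison is specified.
- **A reader might infer that the augmentation hypothesis goes untested.** It does not. The clause "IPILIMUMAB may augment the T cell-mediated immune response generated by PROSTVAC by blocking the inhibitory signal of the CTLA-4 checkpoint" names no compartment, and the arms are compared in tissue. The stated objectives ask about the effect of each regimen.
- **The endpoints carry no decision.** This stands. Two are exploratory and one is a descriptive secondary, no sample size rests on them, and power at 13 per arm is low. That supports estimates with intervals and a modest weight. It does not favour the planned within-arm tests, which use the same 13 patients per arm to answer a different question.
- **The harm needs a misreading that the plan does not prescribe.** True. But with no contrast named, any statement about the combination in blood would rest on informal comparison or on a test chosen after the data are seen.

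**Conclusion.** The concern holds as a gap in specification. No between-arm contrast is named for antigen-specific T cells, Luminex or flow cytometry, so followed as written the randomised C-versus-A comparison is not made in blood. The aggregate T-cell fit mixes unvaccinated patients into vaccine-specific responses.

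The size depends on unknown SDs. Over equal true changes of 0.3 to 0.8 SD with 13 per arm, within-arm significance would point to a spurious difference in about a quarter to a half of trials. These figures assume normal changes, independent arms and a single test per arm; several visits, antigens and analytes would add further tests.

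Severity: consider. The primary tissue analysis is unaffected.

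**What to change.** - **8.5.3, antigen-specific T cells:** fit one model to all three arms with arm, visit, arm-by-visit and a random subject effect. Name the difference in change from screening to the pre-RP sample as the contrast: C − A first, C − B second, each with a 95% CI and labelled exploratory.
- **8.5.3, Luminex:** state the same model and contrasts.
- **8.5.2, flow cytometry:** give changes by arm, with the same two contrasts and CIs.
- **Existing output:** keep within-arm changes as description, and do not rely on the aggregate fit for PSA- or vector-specific responses.
- **In the same edit:** reconcile the four visits in 8.5.3 with the three sampling times in 7.1.2.2 and with the immune-monitoring visits in Section 6.1 (up to 9 weeks after RP, five in Arms A and C and four in Arm B).

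The cost is SAP wording and a little more analysis, with no extra patients or samples. Intervals will be wide, as shown above. The pre-RP sample falls 14 days earlier in Arm B (Day 43 against Day 57), so C − A is the cleaner contrast and C − B should be read with that noted. Outcome scale and baseline handling (covariate or constrained) are the trial statistician's choice, to be fixed before the data are seen.

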#### 3.1 Characteristics

This is a multicentered, open label, randomized phase II trial of PROSTVAC or ipilimumab or the combination of PROSTVAC and ipilimumab as neoadjuvant therapy in patients with localized PC. Eligible patients will be randomized to PROSTVAC monotherapy (Arm A), ipilimumab monotherapy (Arm B), or combination therapy with both PROSTVAC and ipilimumab (Arm C), prior to RP. In arm A, PROSTVAC- V will be administered subcutaneously as the primary vaccine on Day 1, which will be followed 2 weeks later with a series 2 PROSTVAC-F subcutaneous administrations, given 3 weeks apart (Day 15 and 36). In arm B, Ipilimumab will be administered twice, at a dose of 3 mg/kg, 3 weeks apart (Day 1 and 22). In arm C, PROSTVAC will be administered in the same schedule as given in arm A; Ipilimumab will be administered on the same days as PROSTVAC-F. In all three arms, RP will occur 21 days, or 3 weeks, following the final study treatment administration. No further study therapy will be administered following RP.

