#### 7.1.2.2 Antigen-specific T Cell Immunity in Peripheral Blood

To assess antigen-specific T cell immunity in the peripheral blood, indicated by the T cell response to PSA-3, peripheral blood samples will be collected from subjects at the screening visit, prior to RP and at 9 weeks post-RP. The frequency of PSA, TAA and vector specific T cells will be enumerated by interferon gamma (IFN- $\gamma$ ) enzyme-linked immunospot (ELISPOT) assays using established methods (41).

T-cell proliferation assay will also be measured at the same timepoints the antigen-specific T cell response by co-culturing previously cryopreserved PBMCs in triplicate with PSA, TAA, viral vector or PHA-L, and assessing with a standardized [ $^3\text{H}$ ] thymidine proliferation assay (48),(49).

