### 8.5.1 Primary Analysis (or Analysis of Primary Endpoint)

The primary analysis for immune response within the prostate will include all enrolled subjects who receive at least 1 dose of PROSTVAC or ipilimumab in any of the treatment arms, and undergo RP. Analysis will be done for each arm separately as well as aggregate for all treatment arms.

CD3+ T cell infiltration will be assessed by IHC staining, and quantitated by the number of CD3+ T cells/ $\mu\text{m}^2$ . Therefore, the number of T cells will be normalized per unit area. For the analysis of the primary endpoint, T cells will be enumerated from tumor/benign tissue interface (from here on referred to as the “tumor interface”). Subjects will be considered to have a “positive” response if they exhibit a  $\geq 2$ -fold increase in CD3+ T cell infiltration, and a “negative” response if they exhibit a  $< 2$ -fold increase. The proportion of patients who have “positive” responses will be reported, with 95% confidence intervals. Furthermore, the positive response rate will be compared between the combination arm vs. the monotherapy arms (pooling the two monotherapy arms together) via two-sample proportion test. Pairwise comparisons among the three arms will also be performed by two-sample proportion test. No multiple testing adjustments will be performed. Additional analyses will be performed for assessment of response at the tumor center and benign glands and will be reported similarly to the primary endpoint.

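### For vector-specific T cells, the three-arm aggregate in Section 8.5.3 mixes vaccinated men with Arm B, which receives no viral vector; pooling Arms A and C only would match exposure and be more precise.

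*Combined protocol and SAP*

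**What the plan says.** Section 8.5.3 describes the analysis of T-cell immunity in blood: "Assessment of change from baseline in antigen-specific T-cell immunity in the blood will be performed using repeated measure analysis of variance (ANOVA) methods". On its terms it says that "the mixed model will include four visits (up to 9 weeks post-RP) and subject as a random effect". No arm term and no arm-by-visit term is listed. The same bullet ends: "The above analysis will be done for each arm separately as well as aggregate".

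Section 8.5.3 does not define the aggregate, but Section 8.5.1 uses the same phrase and spells it out: "Analysis will be done for each arm separately as well as aggregate for all treatment arms".

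Section 7.1.2.2 lists the antigens: "The frequency of PSA, TAA and vector specific T cells will be enumerated by interferon gamma" ELISPOT. The proliferation assay in that section also has viral vector among its stimulants.

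Sections 3.1 and 3.4 and Table 2 give PROSTVAC-V and PROSTVAC-F to Arms A and C. Of Arm B, Section 3.1 says: "In arm B, Ipilimumab will be administered twice"; no vaccine is scheduled for that arm. No sentence in Section 8.5.3 treats vector antigens differently from PSA or other tumor-associated antigens.

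**The concern.** A vaccine-induced response to the vector cannot arise in men who were not given the vector. For vector-specific T cells, the mean change over all three arms is therefore neither the change after vaccination nor a contrast between vaccinated and unvaccinated men. If Arm B does not change, its men pull the mean toward zero, and the difference between exposed and unexposed men adds to the spread.

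PSA and tumor-associated antigens are different. The rationale in the Abstract hypothesizes that each agent alone can induce a specific immune response in tumor and blood, so a three-arm aggregate for those antigens is not diluted by design.

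What is at stake is the precision and meaning of one exploratory summary. No decision rule depends on it.

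**Working it through.** **Plan's own figures.** The documents state no power, effect size or alpha for this analysis, so there is no figure to reproduce for it. The arm size comes from Section 8.2, which gives 13 evaluable men per arm and 7% dropout: 3 × 13 = 39, and 39 / 0.93 = 41.9, which rounds up to the stated 42.

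**Inputs.**
- From the documents: 1:1:1 allocation (Section 3.6) and 13 evaluable men per arm (Section 8.2, set for the tissue endpoint and borrowed here). Arms A and C together have 26 men; all arms have 39.
- Assumed: mean change d, in units of the within-arm SD, equal in Arms A and C; mean change zero in Arm B; equal SDs; two-sided alpha 0.05. A one-sample t-test on change from baseline stands in for a single baseline-to-visit contrast of the mixed model.

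**Step 1, mean.** Aggregate mean = (26 × d + 13 × 0) / 39 = 2d/3.

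**Step 2, spread.** In a 2:1 mixture of means d and 0, the between-group variance is (2/3)(1/3)d² = 2d²/9. Aggregate SD = √(1 + 2d²/9). At d = 0.5 this is √1.0556 = 1.027.

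**Step 3, noncentrality (mean / SD × √n) at d = 0.5.**
- Arms A and C pooled: 0.5 × √26 = 2.55
- All arms: (0.333 / 1.027) × √39 = 2.03
- One vaccine arm: 0.5 × √13 = 1.80

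**Step 4, power from the noncentral t distribution.**

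| Change d in A and C | A and C pooled (n = 26) | All arms (n = 39) | One vaccine arm (n = 13) |
|---|---|---|---|
| 0.4 SD | 50% | 36% | 26% |
| 0.5 SD | 69% | 51% | 38% |
| 0.6 SD | 84% | 65% | 51% |
| 1.0 SD | 99.8% | 96% | 91% |

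**Step 5, sensitivity to Arm B.** Suppose Arm B shows a fraction f of the vaccinated change. The aggregate mean is then (2 + f)d/3. Ignoring the small between-arm variance, the aggregate matches pooled A and C when √39 × (2 + f)/3 = √26, so f = √6 − 2 = 0.449. Below about 45% the aggregate loses power; above it, the extra 13 men help.

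**The case against.** The strongest reply is that the sentence at issue already plans each arm separately. Arm A and Arm C vector responses will be seen undiluted, and Arm B will be seen alone. That stands, and it is the main reason the point is small.

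Second, the power comparison is with a pooled A and C analysis that the plan does not contain. A reader might infer that the aggregate is weaker than the planned analyses of Arm A or Arm C. It is not: at 0.5 SD it has 51% power against 38% for a single 13-man arm, and its noncentrality stays larger up to a change of about 1.22 SD. The loss is only against the 26 vaccinated men taken together.

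Third, a reader might extend the point to antibodies, since Section 8.5.3 also says: "Measurement of antibodies to PSA, TAA and the viral vector may be performed using peptide/protein arrays, standard ELISA assays or flow cytometry". The documents do not support that. The aggregate sentence closes the T-cell bullet. The humoral bullets are separate; for the antibody measurements they describe clustering and per-patient log2 differences, and they state no aggregate test.

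Fourth, zero change in Arm B is an assumption. The exclusion criteria bar men with an allergy or untoward reaction to earlier smallpox vaccination, not all previously vaccinated men, and the documents do not show that ipilimumab leaves existing vector-reactive T cells unchanged. Equal change in Arms A and C is also assumed, although the protocol hypothesizes that ipilimumab augments the vaccine response. Both stand as limits on the figures.

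Fifth, vector responses may be large, and the gap then narrows to 96% against 99.8% at 1.0 SD. The documents give no T-cell effect size that would settle this.

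**Conclusion.** The point holds for vector-specific T cells only. As written, the aggregate averages two vaccinated arms with one arm that never receives the vector, and the listed model terms do not separate them. If Arm B does not change and Arms A and C change equally, the aggregate understates the vaccinated mean by one third; power at 0.5 SD is 51% rather than the 69% available from the 26 exposed men (36% against 50% at 0.4 SD). These figures also rest on 13 evaluable men per arm, equal SDs, two-sided alpha 0.05 and a one-sample t-test in place of the mixed model.

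The one-third understatement is not a constant: it shrinks with any Arm B response in the same direction. Nor does the point call the three-arm aggregate for PSA and tumor-associated antigens into question. The consequence is small, because the analysis is exploratory and the per-arm results remain. It is worth changing because the plan omits the one pooling that matches exposure.

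**What to change.** Add one sentence to the T-cell bullet of Section 8.5.3: for vector-specific T cells (ELISPOT and proliferation assays), the aggregate analysis pools Arms A and C only, and Arm B is shown separately as the concurrent no-vector comparator. Leave the per-arm analyses and the three-arm aggregate for PSA and tumor-associated antigens as they are. The humoral bullets need no change on this account.

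Naming Arm B has some value of its own, since the untreated reference cohort in Section 8.6 is described as a source of prostatectomy tissue, not of these blood assays. Arm B is unexposed to the vector but not untreated, so Arm C against Arm B is the cleaner reading of the vaccine's contribution.

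Cost: one sentence, with no new samples, assays or patients.
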